10.4. General Methodology

Since this is an exploratory study, no formal hypothesis testing will be performed. Descriptive statistics will be used to tabulate and summarize efficacy and safety outcomes. Background and demographic characteristics will be presented. Continuous variables will be summarized by descriptive statistics (sample size, mean, standard deviation, median, minimum and maximum). Discrete variables will be summarized by frequencies and percentages.

Safety assessments will be made at all study visits and both safety and tolerability will be evaluated by assessing the incidence of DLTs (as defined in Section 8.4.1), AEs and the incidence of SAEs.

AEs, SAEs, and other findings will be summarized by presenting the percentages of subjects with each event for each treatment group. When relevant, the time course of AEs will be presented.

All safety analyses will be presented by dose group and over all subjects. Safety analyses will summarize subjects by the treatment received.

The safety analysis will summarize ocular treatment-emergent AEs (TEAEs) in the study eye for all treated subjects using discrete summaries at the subject- and event-level by system organ class and preferred term. A TEAE will be defined as occurring on or after the day that treatment is initiated. An additional analysis will investigate ocular AEs for the non-study eye. Non-ocular TEAEs will be summarized using discrete summaries at the subject- and event-level by system organ class and preferred term. Treatment-related ocular and non-ocular TEAEs will be summarized similarly. Ocular and non-ocular TEAEs will also be summarized by severity or toxicity grade. Additionally, TEAEs will be summarized by treatment schedule as deemed necessary to better understand the safety profile.

The presence or absence of anti-drug antibodies will be summarized by treatment group.

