## 9.3 Adverse Events

Adverse events (AEs) will be coded using the MedDRA Version 20.0 and will be graded according to the National Center Institute Common Terminology Criteria for AEs (NCI-CTCAE criteria [v4.03]). Uncoded terms will be presented under "SOC uncoded", with their reported term.

Related AEs are defined as events with a relationship to study treatment equal to 'related' or with missing relationship. All AEs related to study drug, related to injection procedure, and related to laser administration will be reported separately.

Adverse events in this section will be tabulated if they are treatment-emergent (TE). Non-TE adverse events will only be included in listing of all adverse events. Adverse events which begin on or after the day the treatment is initiated will be considered as treatment-emergent adverse events (TEAEs). Missing or partial AE start date will be estimated in order to include events in summary tables in case of doubt (see section 4.7 for more details).

Ocular TEAEs are those TEAEs reported as occurring in the eye(s).

All tabulations of adverse events will be presented by cohort, overall, and subgroups (defined in Section 4.4).

An overall summary table of AEs will present the number and percentage of subjects with at least one:

- TEAE
- Serious AE (SAE)
- Related SAE – broken out by study drug, injection procedure and laser related
- Ocular TEAE in the study eye
- Related ocular TEAE in the study eye – broken out by study drug, injection procedure and laser related
- Ocular TEAE in the fellow eye
- Related ocular TEAE in the fellow eye – broken out by study drug, injection procedure and laser related
- Non-ocular TEAE
- Related non-ocular TEAE – broken out by study drug, injection procedure and laser related
- Fatal AE

Tabulations of the number of subjects who experienced TEAEs as well as number of events will be presented by system organ class and preferred term (in descending frequency by SOC and by PT within each SOC). Subjects will only be counted once for each preferred term. In case a subject experienced the same event more than once, the event will be counted only once.

The following tabulations will be presented:

Confidential

- All TEAEs
- Ocular TEAEs in the study eye
- Related ocular TEAEs in the study eye – broken out by study drug, injection procedure and laser related. Three additional tabulations include:
  - Related to study drug and/or injection procedure and/or laser

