  - Related to study drug and/or laser
  - Related to injection procedure that are not related to study drug or laser
- Ocular TEAEs in the fellow eye
- Related ocular TEAEs in the fellow eye – broken out by study drug, injection procedure and laser related, if relevant
- Non-ocular TEAEs
- Related non-ocular TEAEs – broken out by study drug, injection procedure and laser related

In addition, tabulations of the number of subjects who experienced TEAEs as well as number of events will be presented by system organ class, preferred term and worst severity. Subjects will only be counted once for each preferred term. In case a subject experienced the same event more than once, the event with the worst severity will be counted in the summary.

The following tabulations will be presented:

- All TEAEs
- Ocular TEAEs in the study eye
- Related ocular TEAEs in the study eye – broken out by study drug, injection procedure and laser related. Three additional tabulations include:
  - Related to study drug and/or injection procedure and/or laser
  - Related to study drug and/or laser
  - Related to injection procedure that are not related to study drug or laser
- Related non-ocular TEAEs – broken out by study drug, injection procedure and laser related

Listing of all adverse events by cohort will be provided including the subject identifier, age, race, sex, reported term, preferred term, start date (Study Day of Start), stop date (Study Day of Stop), duration, TEAE (Yes/No), DLT (Yes/No), serious (Yes/No), associated eye (OD/OS/OU), severity (Mild/Moderate/Severe/Life-Threatening/Death), relationships (Related/Not Related to each of study drug, injection procedure, and laser administration), outcome, action taken. The adverse event listing will be sorted by treatment arm, subject identifier, start date, and reported term.

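### As worded, SAP 9.3 reduces the number of events to the number of subjects for each preferred term, contrary to the event-level summaries in protocol 10.4

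*SAP*

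**What the plan says.** SAP 9.3 sets out what the TEAE tables contain: "Tabulations of the number of subjects who experienced TEAEs as well as number of events will be presented by system organ class and preferred term". Two counting rules follow. The first is "Subjects will only be counted once for each preferred term". The second is "In case a subject experienced the same event more than once, the event will be counted only once".

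The tables by worst severity again promise subjects and events. Their rule for repeats is "In case a subject experienced the same event more than once, the event with the worst severity will be counted in the summary".

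Protocol 10.4 asks for TEAEs to be summarized "using discrete summaries at the subject- and event-level by system organ class and preferred term". It also allows two further views: "When relevant, the time course of AEs will be presented", and "Additionally, TEAEs will be summarized by treatment schedule as deemed necessary to better understand the safety profile".

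SAP 4.9, which lists changes from the protocol's analyses, names only the tumor response criteria.

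**The concern.** The first counting rule already fixes the subject column. If the second rule means anything more, it governs the event column, and a repeat of the same event in the same subject is dropped there too. The event column then carries no information at PT level, although both documents call for it.

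The primary objective is the safety of repeat doses, one or two laser applications and one or two cycles. Cohorts 10 to 12 are planned for two cycles of three doses (Cohort 10 once growth is established). Under protocol 8.2.1 the start of Cycle 2 depends on how far inflammation from Cycle 1 has settled. Whether an event comes back with further administrations is therefore a central safety question, and an event count is the simplest summary that bears on it.

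**Working it through.** The plan states no figure to reproduce. The check is a reading of the rule, followed by a bound and an illustration.

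**1. The two readings side by side.** Take two subjects from a two-cycle cohort. One has uveitis once. The other has a separate uveitis record after each of six administrations.

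| | Subject column | Event column |
|---|---|---|
| Once-only rule applied to events (literal) | 2 | 1 + 1 = 2 |
| Every record counted | 2 | 1 + 6 = 7 |

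On the literal reading the two columns always agree in a PT row. In a SOC row the event count becomes the number of distinct subject-and-PT pairs. The SAP does not say whether the same event means the same PT, the same reported term or one continuing episode; the figures here take it as the same PT.

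**2. Whether other planned AE tables supply what is lost.**
- The reporting windows in SAP 11.2 have no Cycle 2 or additional-therapy treatment visits.
- SAP 9.1 summarizes exposure at Days 1, 8 and 15 only.
- The table list in SAP 11.3.1 has no TEAE table by cycle or treatment day.
- The AE listing (SAP 9.3; Listing 16.3.3.1) gives each event with start and stop day, severity and relatedness, so the information survives there.

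**3. The bound.** With one record per administration, the true-to-counted ratio for one subject and term is the number of administrations.
- One three-dose cycle: 3 / 1 = 3-fold.
- Two cycles: 2 × 3 = 6 administrations, so 6 / 1 = 6-fold.
- A single-dose subject given one course of additional AU-011 (protocol 8.3.3): 1 + 3 = 4 administrations, so this subject is not exempt.

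**4. Illustration.** Let K be the treatment days, n the subjects, and p an independent chance of the same PT on each treatment day. Occurrences = n × K × p. Counted under the literal rule = n × [1 − (1 − p)^K]. The documents give no AE rates, so p is an assumption, shown over a range. The n are the planned maxima for Cohort 9 (12) and Cohort 12 (15).

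| K | n | p | Occurrences | Counted | Share lost |
|---|---|---|---|---|---|
| 3 | 12 | 0.1 | 3.6 | 3.25 | 9.7% |
| 3 | 12 | 0.3 | 10.8 | 7.88 | 27.0% |
| 3 | 12 | 0.5 | 18.0 | 10.50 | 41.7% |
| 3 | 12 | 1 | 36 | 12 | 66.7% |
| 6 | 15 | 0.1 | 9.0 | 7.03 | 21.9% |
| 6 | 15 | 0.3 | 27.0 | 13.24 | 51.0% |
| 6 | 15 | 0.5 | 45.0 | 14.77 | 67.2% |
| 6 | 15 | 1 | 90 | 15 | 83.3% |

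The rows with p = 1 are the 3-fold and 6-fold bounds.

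**The case against.** The sentence may be loose drafting that restates the subject rule; the literal reading makes the promised event column pointless, which is hardly what was intended. Protocol 10.4 does not define an event count either, so the conflict exists on one reading only. This is fair as to intent. It does not remove the problem: a programmer who follows the text produces a different table from one who follows the presumed intent.

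Other outputs cover part of the ground, and this stands. Table 14.3.5.3 summarizes IOP increase on treatment days. SAP 9.6.2 tabulates anterior chamber cells and vitreous haze at each visit, and the visits include Days 1, 2, 8, 9, 15 and 16. First-cycle inflammation is therefore visible by visit. The same cannot be said for Cycle 2, which has no reporting windows.

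The bounds need a fresh AE record after every administration. Doses are a week apart and events are followed until they resolve, so inflammation that has not cleared could be one continuing record, and one event under either rule. The documents do not say how such episodes are recorded. This also stands, and the 3-fold and 6-fold figures are ceilings.

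A reader might infer that single-dose cohorts escape the undercount, so that the rule shrinks differences between regimens. The documents do not support that. Protocol 8.3.3 offers additional three-dose treatment, with particular mention of subjects first treated at lower doses, and SAP 9 bases the main safety analyses on all data whether or not additional therapy was given.

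**Conclusion.** The point holds for the AE summary tables. Followed as written, SAP 9.3 gives an event count that adds nothing to the subject count at PT level, departs from protocol 10.4 and is not declared in SAP 4.9. It should be corrected because the primary objective concerns repeated exposure.

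The size is limited. The undercount for a subject and term is at most 3-fold over three administrations and 6-fold over six. What is lost in practice depends on AE rates and recording habits that the documents do not give. Subject-level incidence, worst-grade subject counts and the DLT table are unaffected, and the study tests no hypotheses.

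A reader might also conclude that the plan conceals recurrence. It does not: each occurrence stays in the AE listing. The loss is confined to the summaries and is most consequential for Cycle 2 and additional therapy. No claim is made about comparisons between regimens.

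**What to change.** Replace the once-only sentence in SAP 9.3 with wording such as: *Subjects are counted once per SOC and PT; the event column counts every reported TEAE record.* Apply it to all SOC/PT tables. In the worst-severity tables, use the worst grade for the subject column only and count each event under its own grade.

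Add a note that raw event totals must be read with the collection periods in mind. Under protocol 10.2.3.3, Cohorts 1 to 9 report only related events after 30 days from the end of treatment, whereas Cohorts 10 to 12 report all events to the last visit.

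The cost is a few sentences and some programming; no new data are needed. SAP v5.0 postdates the first database lock, so any tables already produced under the literal rule would have to be rerun. A total also does not show when an event recurred. If that is wanted for Cycle 2 or additional therapy, protocol 10.4 already allows summaries by time course or treatment schedule.

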## 9.4 Deaths and Serious Adverse Events

SAEs, related SAEs and fatal AEs will be summarized by system organ class and preferred term. In addition, listings of SAEs and fatal AEs will be provided, similarly to the listing of all AEs.

## 9.5 Clinical Laboratory Determination

Clinical laboratory parameters will be graded (as applicable) using the NCI-CTC version 4.03. Laboratory parameters which cannot be graded will be given the designation of

Confidential

'Normal' or 'Abnormal', where 'Abnormal' is defined as outside of the normal range of [LLN, ULN]. Parameters to be summarized are as follows:

- **Hematology and Differential Panel:** Hemoglobin, hematocrit, Red Blood Cells (RBC), White Blood Cells (WBC), WBC differential, platelets, Mean Corpuscular Volume (MCV).
- **Biochemistry and electrolytes:** Total bilirubin, direct bilirubin, alkaline phosphatase, ALT (SGPT), AST (SGOT), GGT, LDH, blood urea nitrogen (BUN), creatinine, glucose, uric acid, calcium, phosphorus (or phosphate), total protein, albumin, globulin, triglycerides, cholesterol, CK, sodium, potassium, bicarbonate, chloride, and magnesium

For continuous laboratory parameters, summaries of the values and changes from baseline will be presented for each visit by parameter.

Where applicable, the shift from baseline NCI-CTC grade to worst post-baseline NCI-CTC grade will be presented for each parameter. This summary will include all scheduled and unscheduled post-baseline visits in the derivation of worst post-baseline grade.

For parameters without NCI-CTC grading, the shift from baseline abnormality categorization ('Normal', 'Abnormal') to worst post-baseline abnormality categorization ('Normal', 'Abnormal') will be presented for each parameter. This summary will include all scheduled and unscheduled post-baseline visits in the derivation of the worst post-baseline abnormality categorization.

## **9.6 Vital Signs, Physical Findings and Other Observations Related to Safety**

### **9.6.1 Vital Signs**

Descriptive statistics for the actual values and change from baseline values of the vital signs parameters will be summarized at each visit by cohort and overall for the safety population. The vital sign parameters to be summarized are Systolic Blood Pressure (mmHg), Diastolic Blood Pressure (mmHg) and Pulse Rate (beats/min).

### **9.6.2 Slit Lamp Biomicroscopy**

Number and percentage of subjects with normal/abnormal slit lamp biomicroscopy exam in the study eye will be summarized for Motility, Lids/Lacrimal/Lashes, Conjunctiva/Sclera, Cornea, Iris, Pupils, Optic Nerve and Retina parameters at each visit by cohort and overall for the safety population.

Number and percentage of subjects with anterior chamber activity (cells: 0, Trace, 1+, 2+, 3+, 4+) in the study eye will be summarized at each visit by cohort and overall for the safety population.

Number and percentage of subjects with lens status aphakic/pseudo-phakic/phakic as well as complete grade nuclear, posterior subcapsular cataract (PSC) and cortical (0, 1, 2, 3, 4), if phakic, and vitreous haze (0, 1+, 2+, 3+, 4+) in the study eye will be summarized at each visit by cohort and overall for the safety population.

The shift from baseline to week 12, week 52 and week 104 visits for each parameter in the study eye will be presented by cohort and overall for the safety population.

Confidential

### 9.6.3 Visual Field Exam

Results of automated perimetry exam in the study eye and the fellow eye will be provided in a data listing for the safety population.

### 9.6.4 Tonometry

Descriptive statistics of the IOP in the study eye for the actual values and change from baseline values will be summarized at each visit by cohort and overall for the safety population. In case of multiple post-baseline values, only the first value will be taken into account at each visit. All values will be included in the data listing.

### 9.6.5 Fundoscopy

Number and percentage of subjects with normal/abnormal fundoscopy exam in the study eye will be summarized for each visit by cohort and overall for the safety population. The shift from baseline to week 12, week 52 and week 104 visits for fundoscopy exam in the study eye will be presented by cohort and overall for the safety population.

### 9.6.6 Anti-Drug Antibodies

Number and percentage of subjects with positive/negative ADA test result will be summarized at each timepoint by cohort and overall for the safety population.

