5.2. Secondary and Exploratory Objectives

Secondary objectives include evaluating:

- Efficacy of AU-011 with one or two treatment cycles with the maximum safe and feasible dose
- Efficacy and safety of AU-011 in subjects with documented growth
- The immunogenicity of AU-011
- A-scan amplitudes of the internal reflectivity of the lesion at study sites with diagnostic probes
- Optical coherence tomography angiography (OCTA) image changes at study sites with OCTA imaging systems for Cohorts 6 through 9

[figure not shown]

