10.1.2. Screening (Visit 1 [Day -28 to Day 1])

After providing written informed consent, the following procedures will be performed:

- Demographic information
- Eligibility criteria
- Medical and ophthalmic history
- Concomitant medication review

ALL OPHTHALMIC ASSESSMENTS WILL BE PERFORMED ON BOTH EYES AT SCREENING AND THEREAFTER ON THE STUDY EYE ONLY THROUGHOUT THE STUDY, UNLESS OTHERWISE INDICATED.

- Vital signs (blood pressure [BP] and pulse) recorded
- Serum pregnancy test for women of childbearing potential

- BCVA using ETDRS performed prior to dilating eyes (BCVA)
- Slit lamp biomicroscopy
- IOP measured by applanation or tonopen
- Fundoscopy
- Fundus photos
- FA
- EDI-OCT of the macular region and in the region of the tumor
- B-scan
- A-scan (for sites with diagnostic probes only) study eye only
- OCTA of the macular region and in the region of the tumor (Cohorts 6 through 9 only)
- Visual field examination
- Laboratory assessments: Complete Blood Count (CBC) with differential and Comprehensive Metabolic Panel (CMP)
- Blood sample for Anti-drug Antibody (ADA) testing

10.1.3. Single Light-activated AU-011 Administration (or Initial for Repeat) Study Treatment (Visit 2 [Day 1])

During Visit 2, the following procedures will be performed:

- Eligibility criteria review
- Vital signs
- BCVA (Both Eyes)
- Slit lamp biomicroscopy
- IOP
- Fundoscopy
- Fundus photos
- EDI-OCT
- OCTA (Cohorts 6 through 9 only)
- B-scan
- Urine pregnancy test for women of childbearing potential (only if Visit 2 occurs more than 7 days after Visit 1)
- Laboratory assessments: CBC with differential and CMP (only if Visit 2 occurs more than 7 days after Visit 1)
- Administration of Light-activated AU-011 treatment

- Intravitreal injection of AU-011 study drug (Subjects in cohorts 3, 6, 7, 8, 9, 10 [after observation of growth], 11 and 12 receiving 80 μg doses administered as 2 injections of 40 μg in μl will have their IOP measured prior to and after each injection. IOP must be 21 mm Hg or less before each injection can be given and the maximum interval between the two injections is 2 hours. IOP must also be 21 mm Hg or less before the patient is discharged from the clinic).

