10.2.2.4. Anti-Drug Antibodies (ADA)

Anti-drug antibody (ADA) blood samples will be taken at Visit 1 (Screening), Visit 4 (Day 8), Visit 8 (Day 29), Visit 11 (Week 12), and Visit 14 (Week 52). For 3 repeat Light-activated AU-011 administration cohort subjects only, also performed at Visit 6 (Day 15).

Study staff will record the visit numbers and dates, and exact times of AU-011 injections and blood samples taken in source documents. A central laboratory will be used for analyzing and reporting ADA data.

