#### 4.6 Calculated Variables

- Study day 1 is defined as the day when first study treatment was received.
- The baseline is defined as the last assessment done before or on study day 1. For instance, if data was collected at screening and Day 1, then the Day 1 value will be used for baseline
- Time since diagnosis of CM (months) = (month and year of screening – month and year of diagnosis).

Assessments done on the date of study treatment administration are assumed to take place before the administration, unless specified otherwise.

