## 6 Demographic and other Baseline Characteristics

Descriptive statistics with respect to demographics and subject characteristics at baseline will be displayed by cohort, overall, and subgroups (as needed, defined in Section 4.4) for the ITT population.

The variables to be summarized are:

- Age, gender, race, ethnicity
- Iris color, study eye,
- Tumor lesion thickness, tumor largest basal diameter, distance from the fovea, distance from the nerve, Risk factors
- History of Primary Choroidal Melanoma:
  - Eye affected (OS/OD/OU)
  - Time since diagnosis of CM (months)
  - Prior Treatment for CM (Yes/No)
- Vital signs: pulse, systolic and diastolic blood pressure (seated)
- Anti-drug antibody (ADA) sample
- Visual acuity score both in the study eye and in the fellow eye

Confidential

- Ophthalmic history (other than primary CM) both in the study eye and in the fellow eye
- Medical history (other than ophthalmic history)

Medical and ophthalmic history will be coded using the Medical Dictionary for Regulatory Activities (MedDRA) version 20.0 and will be tabulated by system organ class (SOC) and preferred term (PT) by cohort and overall for the ITT population. Multiple occurrences of the same preferred term in one subject will be counted only once. Summary tables will be sorted alphabetically by SOC then by PT within SOC based on descending frequency in the 'overall' column.

Other baseline data, for example, childbearing potential and contraception, serum pregnancy test, etc, will be provided in a data listing.

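### SAP 9.6.6 gives ADA positivity by timepoint but plans no Screening-to-post-dose shift, treatment-emergent rate or ever-positive count

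*SAP*

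**What the plan says.** Protocol 5.2 lists "The immunogenicity of AU-011" among the secondary objectives, and SAP 3.1.2 repeats it. Three parts of the documents bear on how it is met.

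- **Sampling.** Protocol 10.1.2 includes "Blood sample for Anti-drug Antibody (ADA) testing" at Screening. Protocol 10.2.2.4 adds Day 8, Day 29, Week 12 and Week 52, plus Day 15 for cohorts given three doses. Protocol Appendix 4 adds seven samples around a second cycle or additional therapy: one before each of the three administrations and four in follow-up.
- **Analysis.** SAP 9.6.6 states: "Number and percentage of subjects with positive/negative ADA test result will be summarized at each timepoint", split by cohort and in total, on the Safety population. This is delivered as one frequency table by timepoint, Table 14.3.7.3. Protocol 10.4 asks only for a summary of presence or absence by treatment group.
- **Baseline.** SAP 6 includes "Anti-drug antibody (ADA) sample" among the baseline variables, summarized on the ITT population. SAP 4.6 says: "The baseline is defined as the last assessment done before or on study day 1". Protocol 10.1.3 lists no ADA draw on Day 1, so for ADA the baseline is the Screening sample. Listing 16.3.10 gives subject-level ADA results.

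**The concern.** To describe immunogenicity one needs the share of subjects who develop antibody after exposure. That requires comparing each subject's post-dose results with that same subject's pre-dose result. Neither document does this. There is no treatment-emergent definition, no denominator of pre-dose negatives, no shift and no count of subjects positive at any post-dose sample. The SAP plans baseline shifts for laboratory grades (9.5), slit lamp (9.6.2) and fundoscopy (9.6.5), but not for ADA.

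Pre-existing antibody is possible. Protocol 7.2 excludes prior HPV vaccination, but no criterion excludes a subject who is ADA-positive at Screening. A persistent pre-existing positive enters every post-dose percentage, which can make the apparent rate too high. In the other direction, subjects who are transiently positive at different visits are never combined, so any single row can understate how many ever became positive.

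**Working it through.** The documents give no ADA rate, sample size or precision for immunogenicity, so there is no plan figure to reproduce. The rates below are assumptions, used only to show what the planned table can and cannot determine.

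**Inputs.** N = 60 is the approximate planned total (SAP 3.3). Let b be the share positive at Screening (assumed 0 to 30%), and s the share of Screening negatives who convert (assumed 0 or 30%). Let B be the number positive at Screening and P the number positive at a post-dose visit (assumed 50%, so P = 30).

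**1. What a post-dose row mixes.** If pre-existing positives persist and converters are positive at the visit shown, the row reads b + (1 − b)s.

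- b = 20%, s = 0: 0.20 + 0.80 × 0 = 20%, with nobody converting.
- b = 10%, s = 30%: 0.10 + 0.90 × 0.30 = 37%.
- b = 20%, s = 30%: 0.20 + 0.80 × 0.30 = 44%.

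The denominators need care. The 44% is of all subjects, and the matching emergent share of all subjects is 0.80 × 0.30 = 24%. The 30% is of Screening negatives only, so 44% should not be set directly against 30%.

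**2. What can be recovered when the Screening row is also shown.** Knowing B, P and N, the number of converters lies between max(0, P − B) and min(P, N − B). The lower end applies if every Screening positive stays positive, and the upper end if as many as possible have turned negative.

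| b | B | Converters / Screening negatives | Rate |
|---|---|---|---|
| 0 | 0 | 30 / 60 | 50.0% |
| 10% | 6 | 24–30 / 54 | 44.4–55.6% |
| 20% | 12 | 18–30 / 48 | 37.5–62.5% |
| 30% | 18 | 12–30 / 42 | 28.6–71.4% |

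The Screening row shows b but does not identify the conversion rate unless b is zero. A subject-level shift replaces each range with one value.

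**3. Small cohorts.** Escalation cohorts start at 3 subjects. One persistent Screening positive makes every post-dose row in such a cohort read at least 1/3 = 33%, with no induced antibody.

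**4. The cumulative count.** This part does not depend on b. Suppose nobody is positive at Screening and 10% (6 of 60) are positive at each of the four post-dose visits common to all cohorts. The number ever positive lies between 6 (the same subjects each time) and 4 × 6 = 24 (different subjects each time), so 10% to 40%. The by-visit rows cannot say which.

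**5. Other planned outputs.** The baseline ADA summary in SAP 6 is on the ITT population and the post-dose table is on the Safety population. An observed Cohort 10 subject who is never treated belongs to the first and not the second, so the two denominators can differ. SAP 11.2 defines no visit labels for the Appendix 4 samples, which leaves open how they fall under each timepoint.

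**The case against.** A reader might infer that the SAP ignores the Screening sample, or that it counts pre-existing antibody as a response to AU-011. The documents support neither. Screening is a scheduled ADA timepoint and 9.6.6 does not exclude it, ADA is a named baseline variable, and nowhere is a positive result called a response. The table is a descriptive count, and it delivers what Protocol 10.4 asks for.

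The rest of the case against is also fair in part. With about 60 subjects, each subject's sequence can be read from Listing 16.3.10, so conversion and transient positivity are recoverable by hand. The study is exploratory, without hypothesis tests, and no decision rule depends on ADA. The documents do not establish that pre-existing HPV antibody would test positive in this assay. Protocol 4.4 says the capsid loop carrying the main immune epitopes was altered, and vaccinated subjects are excluded.

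These points limit the importance of the gap and leave its size unknown. They do not close it. A listing is not a summary of a secondary objective, the marginal rows still do not give the number converting, and the cumulative count is missing whatever the baseline rate.

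**Conclusion.** The point holds in a limited form. The SAP tabulates ADA prevalence at each timepoint, Screening included, but provides no within-subject comparison and no cumulative count. Its summaries therefore cannot give the treatment-emergent or ever-positive rate that the immunogenicity objective calls for. The risk is one of interpretation; no stated rule miscounts anything.

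The baseline part is nil if no subject is positive at Screening. Under the assumed 10% to 30% Screening positivity and 50% post-dose positivity, the range left open for conversion is about 11 to 43 percentage points wide (55.6 − 44.4 = 11.2; 71.4 − 28.6 = 42.8). Those rates are not in the documents. This is a low-priority improvement to a descriptive analysis and does not threaten the study's main conclusions.

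**What to change.** Add the following to SAP 9.6.6 and Table 14.3.7.3, on the Safety population, by cohort and overall with the existing subtotals:

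- A shift of pre-dose ADA result (negative, positive, missing) by any post-dose positive result.
- Treatment-emergent ADA: negative at the last sample before first dose and positive at any later sample, among pre-dose-negative subjects with at least one later sample, including the Appendix 4 samples.
- Pre-dose-positive subjects shown separately, with boosting if titres exist, so that a rise in existing antibody is not lost.
- For second-cycle or additional-therapy results, that cycle's own pre-dose sample as the reference.

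A footnote should say that in Cohort 10 the Screening sample may be old by the first dose, because the observation visits omit ADA.

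No new data are needed. The cost is one extra table. Denominators will be 3 or fewer in many escalation cohorts, so the text should rely on the overall and subtotal columns. SAP v5.0 already postdates the first database lock (25 Aug. 2021), so the addition should be labelled as made after that lock.
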